comprised not only of material strain, but also psychological strain (Tucker-Seeley & Thorpe, 2019). Perceived financial strain from caregiving is associated with role overload and burden (Andren & Elmstahl, 2007; Lai, 2012; Liu, Dokos, Fauth, Lee, & Zarit, 2019). For low-income caregivers, out-of-pocket spending on caregiving, combined with periodic or permanent lost wages, can compound financial strain over a lifetime. **Hispanic caregivers have higher out-of-pocket caregiving costs relative to their income than non- Hispanic caregivers.** Whereas out-of-pocket expenditures on caregiving—regardless of the care recipient's cognitive status—consumes 20% of caregivers' annual income and costs \$6,954 per year on average, these costs comprise nearly half (47%) the income of Hispanic women who provide care and total \$10,704 annually (Rainville et al., 2016). Relative to the average caregiver (i.e., caregiver of any race/ethnicity), Hispanic women who provide care spend \$1,849 more on household items (e.g. home modifications for safety, home repairs) and \$1,849 on education, legal, and travel expenses (e.g., retrofitting vehicles to accommodate wheelchairs) per year. Higher caregiving costs are in-part due to a preference among Hispanic families for older family members to receive care in the community, rather than in skilled nursing facilities, and often within a shared household (Angel & Berlinger, 2018; Scharlach et al., 2006). A growing number of Hispanic families are likely to care for someone living with dementia. Hispanics are 50% more likely to experience dementia and current projections suggest there will be an 832% growth in the number of Hispanics who live with dementia by 2060 (Alzheimer's Association, 2019; Wu, Vega, Resendez, & Jin, 2016). Given the anticipated growth in the number of Hispanic families living with dementia, financial disadvantages that are already experienced by U.S. Hispanics, and the high costs from caregiving, dementia has been described as "the perfect storm" for financial hardship among U.S. Hispanics (Wu et al., 2016). **Caregivers struggle to access community-based resources and benefits that could be used to displace out-of-pocket expenditures related to caregiving.** Community-based (social support) systems that serve family caregivers and older adults are de-centralized and difficult to navigate (Funk, Dansereau, & Novek, 2019; Meyer, 2017). Although most service-seeking caregivers need at least some assistance with legal and financial matters (e.g., seeking health and non-health benefits), Hispanic caregivers are less likely to use social supports for themselves than non-Hispanic caregivers (Martindale-Adams, Nichols, Zuber, Burns, & Graney, 2016; Shrestha et al., 2011). Qualitative research reveals that Hispanic caregivers know that community-based services exist to support caregivers, but perceive accessing these resources overly burdensome relative to their perceived value (Scharlach et al., 2006). Hispanic caregivers also identify a need for more culturally-relevant services, especially those based on Mexican cultural norms. As such, compared to non-Hispanics, Hispanic caregivers may face more barriers to accessing services and supports like those provided through the National Family Caregiver Support Program that could be used to off-set some of the out-of-pocket costs of caregiving (Lepore, Splaine, Bangerter, & Dawson, 2020). **There is an unmet need for programs to alleviate financial hardship among family caregivers.** On April 15th, 2020 the National Academies of Sciences, Engineering and Medicine held a workshop on intervention programs to better support family caregivers. Implementation science expert [name], PhD recommended that the caregiving field develop interventions to address financial hardship using approaches from other fields (2020). In line with this recommendation, the **Confidently Navigating Financial Decisions and Enhancing Financial Wellbeing in Dementia Caregiving (CONFIDENCE)** program draws on successful intervention approaches identified within nursing and gerontological research to lower out-of-pocket caregiving costs and prevent financial hardship among low-income family caregivers. **Given prior research we propose to evaluate an educational program to encourage reduced out-of-pocket spending on caregiving that is developed to be culturally relevant and tailored to the needs of Latino Caregivers. This program will be delivered as a regular service program at the University of Southern California Family Caregiver Support Program. This project is supported by an AARP Foundation grant. Case Western will lead the evaluation of the program to test its preliminary efficacy and feasibility.**

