4.0 Inclusion and Exclusion Criteria

Directions: Describe how individuals will be screened for eligibility.

Participants will be asked to either complete an online self-administered survey to determine their eligibility, or to complete eligibility questions by telephone. If participants complete the online form, they will receive a telephone follow up to complete any missing questions, check for fraud (e.g., repeat questions to ensure consistent responses), and complete the verbal consent process.

Using the tables below, describe the inclusion and exclusion criteria that will define who will be included and excluded in your final study sample.

Inclusion	
1.	Age range: from 50 to no upper limit (sponsor criteria)
2.	Physician diagnosis of Alzheimer's Disease or related dementia by a physician at least 6 months ago Able to attend 5, 1.5 to 2 hours group-based lessons over 5 weeks
3.	Latino or Hispanic ethnicity
4.	Able to attend 5, 1.5 to 2 hours group-based lessons over 5 weeks

Exclusion	
1.	Unreliable access to email, a computer, and internet access
2.	Does not speak and read English
3.	Previously attended CONFIDENCE program

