timeline for the Baseline survey. If so, we will continue to allow them to participate in the study without complete they daily spending surveys, so long as the Baseline survey is completed prior to the first intervention session. This will enable us to still collect data about outcomes besides out-of-pocket costs of care. A follow up survey will be sent immediately after the participant completes the intervention (within 48 hours) and will also ask about participant satisfaction with CONFIDENCE. A second follow up survey will be sent 8 weeks after the intervention is complete. After the participant completes the second follow up survey, they will receive a second set of daily spending diaries administered in the same way as the first set of diaries. Follow up surveys are expected to take approximately 20 to 30 minutes to complete. Participants will receive up to 5 reminders to complete the baseline and follow up surveys, include 3 emails prompts and up to 2 phone calls. Participants will receive a text message reminder, if they choose, reminding them to complete daily spending surveys each night. **Qualitative interviews.** Up to 15 participants will also be asked to participate in a one-on-one qualitative, in-depth, semi-structured interview as well about their experiences with the program, which is expected to take approximately 45 minutes depending on how much the participant would like to share. Selection of interview participants will be based on purposeful sampling, with the goal of recruiting a qualitative sample that includes a range of care experiences according to participant gender, age, employment status, and kin relationship to the person to whom care is provided. Interviews will be completed over Zoom and recorded and later transcribed. Participants will be invited to complete this interview after completing the CONFIDENCE program. If the participant agrees to participate, they will receive a study information sheet by email prior to attending the interview and will review this information sheet before completing the interview. **Payment for surveys and qualitative interviews.** Amazon gift cards will be sent to participants by email for each study activity (surveys and interviews). We will pay participants for the baseline and first set of diaries surveys within a week of when the first set of diaries are due. A second payment will be administered within a week of the first follow up survey being completed. The remaining payments will be sent the week of the second set of diary surveys are due/completed. Payment for interviews will be sent within 1 week of completing the interview. Participants may earn up to \$125 for participating, or \$150 if they complete the qualitative interview. Participants may earn \$25 for each study activity. **Fidelity.** Fidelity will be monitored by an observer (PI or research assistant) and the CONFIDENCE program facilitators. We will monitor one randomly selected CONFIDENCE lesson for each cohort. The selected lesson will be based on Stata's random number generator. The facilitators will know in advance of each lesson if selected for monitoring so they may record lesson. The facilitator will be sent a survey within 24 hours of completing selected sessions to self-monitor delivery. Fidelity surveys will be sent by the PI using REDCap. Session recordings will be stored in the USC CONFIDENCE Office 365 Shared folder and deleted once fidelity forms are completed. The research assistant or PI will watch the recording and complete the fidelity survey within 2 weeks of the lesson taking place. **Attendance.** The USC facilitator will monitor attendance at CONFIDENCE sessions and will store this information in a shared Office 365 folder. The study team will extract information about attendance from study participants from Excel files where attendance is marked and enter it into REDCap for study participants. **Comparison of registrant demographics and study participants.** In addition to data collected from surveys, we will compare the demographic characteristics of individuals who register for CONFIDENCE to participate in the educational program alone with those of study participants. This information can help to inform future recruitment methods by helping the study team understand differences in the characteristics of those who choose to participate in research and those who do not. As a part of their funder's requirements, USC must report on demographic characteristics of program participants to the sponsor. They currently collect this information using the Eventbrite registration page. The Case Western investigators will already have access to the Eventbrite form information to identify participants who are interested in participating in the research study. To compare the characteristics of study participants to non-study participants, we will download Excel files directly from Eventbrite onto an encrypted university Box folder, and add an indicator variable to indicate whether or not individual registrants were in the research study. Once this occurs, all identifiable information will be removed from Excel files and the file will be saved so we can conduct analyses and compare characteristics of study and non-study participants. **Participant safety and monitoring adverse events.** *Adverse events.* Adverse events and protocol deviations will be recorded on an adverse event form by the study team member (PI or RA) who first observes this event. Adverse events pertaining to participant safety and confidentiality will be promptly reported by the PI by phone. Where the RA or PI suspects risk of harm to self or others, this will be reported to USC PI [name], who is a licensed clinical psychologist with extensive experience working with caregivers. [name] is the director of the USC Family Caregiver Support Program where CONFIDENCE is being administered. She will reach out to the participant by phone to conduct further assessment and a safety plan. All protocol deviations and adverse events will be promptly reported to the Institutional Review Board by the PI. Serious adverse events will be reported within 24-hours. **Data and Safety Monitoring.** The PI will complete a Data Safety Monitoring Report every 6 months of the study. The Data Safety Monitoring Report will include the following core elements: a) Progress towards enrollment and participant retention; b) Participant characteristics for enrolled and retained participants (e.g., age, race, ethnicity, gender, aspects of the caregiving situation) according to intervention status; and c) Documentation of adverse events, serious adverse events, and unanticipated problems, as defined below, including resolution of these events and study protocol modifications. This report will not contain any participant identifiers. This report will be shared with the USC PI for review.

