17.0 Data Analysis Plan

Directions: Describe the data analysis plan, including any statistical procedures. If applicable, provide a power analysis, and study/safety endpoints. Directions: Describe the data analysis plan, including any statistical procedures. If applicable, provide a power analysis, and study/safety endpoints

Participant Demographic Characteristics

Participant characteristics, including age, gender, race, ethnicity, educational attainment, income, employment status, kin relationship to recipient, length of time caregiving, hours of caregiving, and whether the care recipient and caregiver live together will be reported using frequencies, percentages, means, and standards of deviation. *Comparison of Study and non-study participants*. Demographic characteristics of study and non-study participants collected from Eventbrite will be compared using t-test and chi-squared bivariate analyses, as well as frequencies and percentages. **Outcome Measures** *Self-Efficacy (primary outcome)*. Self-efficacy is measured using the Caregiver Self-Efficacy Scale. This 8-item scale combines domains of self-efficacy (e.g., managing behavioral symptoms, accessing respite, and controlling upsetting thoughts. It demonstrates high reliability ($\alpha=0.89$) and good test-retest reliability (0.73). Participants rate the extent to which they are “Not confident at all” (1) to “Totally confident” (10). Scores range from 8 (lowest) to 80 (highest).³⁵ *Resourcefulness (primary outcome)*. Resourcefulness is measured using the 19-item learned resourcefulness scale designed for family caregivers ($\alpha=0.81$). This scale has two factors: one focused on help-seeking and another on self-help. Caregivers are asked the frequency at which they use different strategies to manage challenges, and may respond: . Items are added together to create a total score. Scores range from 0 to 24. Permission was received by the scale’s author to use this tool on April 21, 2022.

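### The registrant comparison asks who chooses research, but its single in-study indicator groups screened-out and ineligible registrants with those who declined

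*Combined protocol and SAP*

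**What the plan says.** Under the comparison of registrant demographics, Section 12.0 gives the purpose as understanding "differences in the characteristics of those who choose to participate in research and those who do not", so as to inform later recruitment. The comparison is described this way: "we will compare the demographic characteristics of individuals who register for CONFIDENCE to participate in the educational program alone with those of study participants". In practice the team downloads the Eventbrite file and will "add an indicator variable to indicate whether or not individual registrants were in the research study". After that, "all identifiable information will be removed from Excel files".

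Section 17.0 gives the analysis: "Demographic characteristics of study and non-study participants collected from Eventbrite will be compared using t-test and chi-squared bivariate analyses", together with frequencies and percentages. Neither section limits the comparator to people who could have enrolled.

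Section 4.0 restricts study entry to caregivers aged 50 or over, a rule it labels as the sponsor's, and requires "Latino or Hispanic ethnicity". It also sets conditions on the dementia diagnosis, English, internet access and earlier attendance. Sections 12.0 and 24.0 let caregivers attend the program whether or not they join the study.

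**The concern.** The stated question is about choice, but the indicator records enrolment. Enrolment depends on choice and on eligibility, and the single code cannot separate them. Two groups are misplaced.

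- Registrants who said yes and were then screened out. They made the choice under study but are coded with those who said no. This holds whatever the age and ethnicity mix of registrants.
- Registrants under 50 or non-Latino, if there are any. They could not have enrolled, so their presence in the comparator reflects the entry rule.

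The ethnicity contrast would be recognised easily, because every study participant is Latino or Hispanic by criterion. An age contrast is less transparent. Younger registrants pull the comparator mean down, which can create an age difference that is only the entry rule, or offset a real one among eligible people. At stake is the advice on recruitment drawn from the table. Once identifiers are removed, a screening outcome that was not coded beforehand is hard to add.

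**Working it through.** **Group sizes.** Section 8.0 expects 12 cohorts with 5 enrolled in each: 12 × 5 = 60, which reproduces the plan's goal. It puts this at about one third of sign-ups, so 60 ÷ (1/3) = 180 registrants. Section 12.0 allows up to 15 per session, and 12 × 15 = 180 agrees. That leaves 180 − 60 = 120 registrants outside the study.

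**Assumptions not in the documents.** Eventbrite records age as a continuous value; ages are normal with mean m and SD s; the test is two-sided at 0.05 (Section 17.0 gives 0.05 only for the outcome tests). The share under 50 is Φ((50 − m)/s). For example, m = 65 and s = 10 give Φ(−1.5) = 6.7%.

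**Expected gap, by hand.** Take m = 65, s = 10, and 60 people enrolled at random from those aged 50 or over, so that choice is unrelated to age. The normal density at 1.5 is 0.1295.

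- Mean age of those 50 or over: 65 + 10 × 0.1295/0.9332 = 66.4.
- Mean age of those under 50: 65 − 10 × 0.1295/0.0668 = 45.6.
- Under-50 share of the comparator: 180 × 0.0668/120 = 10.0%.
- Expected gap: 0.100 × (66.4 − 45.6) = 2.1 years, produced entirely by the entry rule.

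**Creating a difference.** The same set-up was simulated (10,000 runs per row, two-sample t-test). Repeat runs differ by about one percentage point.

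| Assumed ages (m, s) | Share of 180 under 50 | Mean gap, years | Significant, all 120 | Significant, comparator 50+ | Comparator size if 50+ |
|---|---|---|---|---|---|
| 80, 8 | 0.0% | 0.0 | 5% | about 5% | 120 |
| 68, 8 | 1.2% | 0.4 | 6% | about 5% | 118 |
| 65, 8 | 3.0% | 0.8 | 9-10% | about 5% | 115 |
| 65, 10 | 6.7% | 2.1 | 24-25% | about 5% | 108 |
| 62, 10 | 11.5% | 3.3 | 55% | about 5% | 99 |

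**Hiding a difference.** Now let older eligible people join less often, with an assumed joining weight of exp(−0.04 × age) among those 50 or over (4,000 runs per case).

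- 3.0% under 50: the gap reads −1.7 instead of −2.5 years, detected in about 25% instead of 58-60% of runs.
- 6.7% under 50: −1.4 instead of −3.6 years, 12% instead of 74%.
- 11.5% under 50: +0.3 instead of −3.2 years, 3% instead of 67%.

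**Precision cost of restricting.** The standardised difference detectable with 80% power is about (1.960 + 0.842) × √(1/60 + 1/n). For n = 120 this is 2.802 × 0.1581 = 0.443, and for n = 99 it is 2.802 × 0.1636 = 0.458. Using the t distribution, the values are 0.445 and 0.461.

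**The case against.** The best reply is that few or no registrants may be under 50 or non-Latino. Section 3.0 describes the program as "tailored to the needs of Latino Caregivers", Section 4.0 attributes the age rule to the sponsor, and the added outreach in Section 8.0 is aimed at Latino caregivers aged 50 or over. At 1.2% under 50 the effect is close to nominal. This stands as a limit on size. On the other side, Sections 3.0 and 12.0 present the program as a regular service. Section 5.0 lets program attenders be interviewed only if they meet the criteria, so attendance does not guarantee eligibility. That condition could concern diagnosis, language or internet access, so it does not show that anyone under 50 or non-Latino registers. Nor do the 22 ineligible individuals in Section 5.0, whose reasons are not given.

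Second, no section says that Eventbrite collects age, or collects it as a continuous value. If age is banded, the t-test figures fall away, and the planned frequencies could make a younger group visible. If age and ethnicity are kept in the file, an analyst could also restrict on them later. Both points stand, but neither separates screened-out registrants from decliners.

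Third, the phrase about registering for the program alone might be read as meaning only people who did not want research. The indicator that implements it does not make that distinction.

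A reader might also infer that the sign-up interest answer always records choice before screening. Section 8.0 does not support this: people who contact the team directly are taken through eligibility and registered in Eventbrite by a team member.

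**Conclusion.** The mismatch between the purpose and the grouping is in the text and holds. Screened-out registrants are coded with decliners, and nothing keeps people who could not have joined out of the comparator. The size is unknown, because the documents give neither the registrants' age and ethnicity mix nor the number screened out. The simulated figures show sensitivity under assumed age distributions and an assumed joining pattern. They do not estimate what will happen in this trial.

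A reader might infer that the age comparison is certainly biased. The documents do not support that: if registration was limited to Latino caregivers aged 50 or over, the distortion from the age and ethnicity rules disappears and only the mixing of screened-out with declining registrants remains. Nor does the point reach the efficacy analysis, which compares participants with themselves over time. It is a minor point about an ancillary recruitment comparison, worth settling because the correction is cheap and easiest before de-identification.

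**What to change.** State in Section 12.0 who could register for the program. Before identifiers are removed, replace the single indicator with a status code:

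1. enrolled;
2. not enrolled and not known to be ineligible;
3. known to be ineligible, from screening or from Eventbrite age or ethnicity where collected.

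In Section 17.0, compare enrolled participants with registrants who meet the age and ethnicity criteria and are not known to be ineligible. Report the known-ineligible group and ethnicity as counts without a test, since ethnicity is constant by design in the restricted comparison. Limit any table by the sign-up interest answer to people who registered themselves.

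The cost is some wording and one code built from records the team already holds; the screening outcome is the item that must be linked before de-identification. The comparator becomes slightly smaller: in the illustration at 11.5% under 50 it falls from 120 to 99, and the detectable standardised difference rises from 0.445 to 0.461. The restriction is partial, because diagnosis, language and internet access remain unknown for registrants who were never screened. The report should say so.

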 - Other. *Please specify:* The research assistant or PI will contact participants who enroll in the Eventbrite page to register for the program with the USC Family Caregiver Support Program. Participants are asked about their interest in participating in a research study when they sign up to attend CONFIDENCE. Those who indicate an interest in the study will receive a follow up phone call and/or email from the study team to tell them more about the study and check eligibility if interested. Participants who began participation at UT Health San Antonio will also be contacted to ask about continuing their participation in the study at Case Western. We will reconsent these participants prior to their continuing to engage in study activities. *ADDITIONAL METHODS OF RECRUITMENT SUBMITTED 10/2022:* To hasten the pace of recruitment, the study team is also requesting to submit an article to *La Presna*, a Spanish/English newspaper in the northern Ohio and southeast Michigan regions that describes the program and study. We also prepared talking points that USC FCSC family care navigators can share about the program and the study if they wish to. Lastly, the PI, with permission of the USC FCSC will also send an individual email and/or phone call to likely eligible participants (50+, Latino). The USC FCSC will send a password-protected file with caregivers' name, email, and phone number to the PI, who will contact caregivers directly to learn if they may be interested in participating in the program and/or the study. *ADDITIONAL METHODS OF RECRUITMENT SUBMITTED 11/2022:* We will also work with Banner Health Institute's Alzheimer's Prevention Registry to identify potential participants. Individuals identifying as a caregiver sign up to receive email blasts from Banner Health and may review information about studies they may be interested in a website. Persons who are interested then indicate their interest, and provide the study team their name, email, and phone number to reach them. This information is made available in a portal where the study team will whether they contacted the participant.
2. Describe when, where, how and by whom potential research participants will be recruited. Individuals involved in recruitment should be identified by role and not by name (e.g. study coordinator, co-investigator, research assistant).

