See above. Participants will also be able to contact the study team directly, such as by calling or emailing the research assistant after seeing a study flyer or social media post. If this occurs, the study team member will not only complete study eligibility procedures,

but register participants in the Eventbrite system to reserve a CONFIDENCE spot for them. For those caregivers who receive a letter or phone call from the PI or who sign up on the Banner Health Institute site, the PI will contact the participant by telephone and/or email up to 3 times to share more information about the study and/or enroll the participant.

3. Describe the feasibility of recruiting the required number of suitable research participants within the agreed recruitment period. For example, how many potential research participants do you have access to?

USC will complete 12 cohorts of the CONFIDENCE intervention from September 2022 to June 2023, where cohorts will be held monthly except for 3 months where USC will run 2 cohorts simultaneously. We expect to enroll N=5 caregivers per cohort, or about 1/3 of caregivers who sign up to attend the program, to reach our recruitment goal N=60 caregivers.

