Overall. This study uses a single arm pre- and post-test design with three data collection points (baseline and two follow up) to evaluate the preliminary efficacy, acceptability, and feasibility of delivering an intervention to lower the out-of-pocket spending on caregiving for Latino caregivers to persons living with dementia. Data will be primarily collected using survey research methods, including “daily diary” methods (N=60). We also plan to collect qualitative semi-structured interviews with participants (N=15), as well as fidelity information about the delivery of the intervention. Participation will take approximately 10 weeks from baseline to completion. **Enrollment.** Participants will enroll in the CONFIDENCE program using an Eventbrite link that will be shared as a part of regular services offered by the University of Southern California Family Caregiver Support Center. When a participant registers for the CONFIDENCE program, they will be asked if they are interested in participating in the research study. Participation in the research study is optional; caregivers do not need to enroll in the study to attend the program. If a caregiver indicated interest in this research, the research assistant or PI will reach out by phone and email (up to 4 contacts) to tell the caregiver more about the study and determine eligibility. The participant may choose to complete the eligibility form online or by phone. Even if the participant completes the eligibility form online, they will receive a follow up call to ensure they understand the study activities and verbally consent to participate. **Intervention.** Enrolled participants will be asked to attend once weekly group-based sessions for the CONFIDENCE program by Zoom for 5 weeks. Each session will last approximately 1.5 hours each and will require participants to complete up to 1 hour of take-home activities per week. Each session will focus on a different topic (e.g., seeking community resources to displace out-of-pocket spending) meant to help caregivers displace out-of-pocket care costs and reduce financial strain. There are five sessions (5 weeks) total to the CONFIDENCE program. Sessions will be led by 2 facilitators with experience in caregiver intervention or else trained by someone with this experience. Up to 15 caregivers may register for each sessions, though we anticipate no more than 10 caregivers to attend each session due to absences.

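### The comparison of study participants with other program registrants mixes recruitment channel and eligibility with the choice to join research

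*Combined protocol and SAP*

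**What the plan says.** Section 12.0 describes the basic route into the study. Caregivers sign up for the program on Eventbrite, and "When a participant registers for the CONFIDENCE program, they will be asked if they are interested in participating in the research study". Those who say yes are contacted and screened.

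Section 8.0 describes other routes:

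- **Flyer and social media.** Some caregivers reach the study directly, "by calling or emailing the research assistant after seeing a study flyer or social media post". The team then screens them and will also "register participants in the Eventbrite system to reserve a CONFIDENCE spot for them".
- **USC list (added 10/2022).** The investigator makes an "individual email and/or phone call to likely eligible participants (50+, Latino") drawn from a file that the USC center supplies. The aim is to "contact caregivers directly to learn if they may be interested in participating in the program and/or the study".
- **Research registry (added 11/2022).** The team works with the "Alzheimer's Prevention Registry to identify potential participants". Interested members pass their contact details to the team.

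For the comparison, Section 12.0 has the team download the Eventbrite files, "add an indicator variable to indicate whether or not individual registrants were in the research study", and then strip identifiable information. The stated use is to learn how people who join research differ from people who do not, as a help to later recruitment. Section 17.0 specifies t-tests, chi-squared tests, frequencies and percentages. Neither section mentions recruitment source, a restriction to eligible people, or stratification.

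**The concern.** A comparison of joiners and non-joiners describes choice only if both groups started from the same place. A caregiver who registered for the program and was then asked about the study did face that choice. A caregiver who answered a study flyer came to the research first and became a registrant because of it. Both carry the same flag in the file.

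Eligibility adds a second layer. Under Section 4.0, participants must be 50 or older and Latino or Hispanic, speak and read English, and have reliable email, computer and internet access. These limits are not stated for program-only registrants. The age limit is marked as a sponsor criterion and so may apply to the whole program, but the documents do not say so. Differences in age or ethnicity could therefore arise from the entry rules alone.

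What is at stake is modest: the advice drawn for future recruitment. A difference that reflects where people were found could be read as a reason why people decline research, or could hide such a reason.

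**Working it through.** **The plan's own figures.** Section 8.0 expects 12 cohorts with 5 participants each, about one third of sign-ups. 12 × 5 = 60, which reproduces the recruitment goal. 5 ÷ (1/3) = 15 sign-ups per cohort, which matches the cap of 15 in Section 12.0. At that cap there are 12 × 15 = 180 registrants, so 60 study and 180 − 60 = 120 non-study. The documents give no sample size, power or effect for this comparison.

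**What the contrast estimates.** Let s be the share of study participants who came by outreach. Let C be the difference between self-registered joiners and non-joiners (choice). Let D be the difference between outreach recruits and non-joiners (channel), in SD units. If all non-study registrants are self-registered:

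expected difference = (1 − s) × C + s × D

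It is pure choice at s = 0 and pure channel only at s = 1. With no true choice effect (C = 0), the bias is s × D. The documents give neither s nor D, so the values below are assumptions.

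**Continuous characteristic, 60 versus 120, two-sided 0.05, C = 0.**

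SE = √[(1 + s(1 − s)D²)/60 + 1/120]; chance of p<0.05 = Φ(sD/SE − 1.96) + Φ(−sD/SE − 1.96).

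Example, s = 0.50 and D = 0.5: bias = 0.25; SE = √(1.0625/60 + 1/120) = 0.161; ratio = 1.55; chance = 34%.

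| Outreach share s | D = 0.3: bias, chance | D = 0.5: bias, chance | D = 0.8: bias, chance |
|---|---|---|---|
| 0 | 0, 5% | 0, 5% | 0, 5% |
| 0.10 | 0.03, 5% | 0.05, 6% | 0.08, 8% |
| 0.25 | 0.08, 8% | 0.13, 12% | 0.20, 23% |
| 0.50 | 0.15, 16% | 0.25, 34% | 0.40, 67% |
| 0.75 | 0.23, 29% | 0.38, 65% | 0.60, 96% |

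**Yes/no characteristic.** Assume 40% in both self-registered groups (no choice effect) and 70% among outreach recruits. The study group then shows p = 0.40(1 − s) + 0.70s. With h = 2·arcsin√p − 2·arcsin√0.40 and z = h × √(60 × 120/180) = 6.32h:

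| s | p | False gap (points) | Chance of p<0.05 |
|---|---|---|---|
| 0.10 | 0.430 | 3.0 | 7% |
| 0.25 | 0.475 | 7.5 | 16% |
| 0.50 | 0.550 | 15.0 | 48% |
| 0.75 | 0.625 | 22.5 | 82% |

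**If outreach also feeds the non-study group.** With a share t of outreach people among non-study registrants and C = 0, the bias is (s − t) × D. For s = 0.50, t = 0.25 and D = 0.5 it is 0.125 SD, half the tabulated 0.25. The tables are therefore upper figures where t is above zero and below s.

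**Cost of restricting to self-registrants.** Detectable difference at 80% power ≈ 2.80 × √[1/(60(1 − s)) + 1/120]. This gives 0.44 SD at s = 0, 0.49 at 0.25, 0.57 at 0.50 and 0.77 at 0.75. Removing ineligible non-study registrants would raise these further, by an amount the documents do not allow one to compute.

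**The case against.** Much of the opposing case is sound.

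- **Choice is still in the contrast.** Self-registration followed by a study-interest question remains a main route, and Section 8.0 plans the 60 as a fraction of program sign-ups. A reader might infer that the comparison measures channel instead of choice. That would need every participant to come by outreach, and nothing in the documents says so.
- **Outreach does not lead automatically into the study group.** Direct contacts are screened, and Sections 10.0 and 24.0 let anyone attend the program without joining the study. Section 5.0 reports 22 ineligible people beside 4 participants carried over from the earlier site. USC-list contacts are offered the program, the study or both. Some outreach contacts may therefore end up as non-study registrants.
- **Team entry into Eventbrite is explicit only for flyer and social media contacts.** Extending it to the registry and the USC list is an inference, though a reasonable one, since participants attend the program and Section 12.0 makes Eventbrite the way in.
- **Recruitment route is not shown to be lost for good.** Section 16.0 keeps a separate eligibility project, and Section 18.0 (Confidentiality of Data) keeps the study key until publication. Nothing says that other Eventbrite fields, such as the study-interest answer, are dropped.
- **The rates and shares above are invented for illustration.** At a 10% share, the false-positive risk barely moves.

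What remains is that the plan provides no step to record source or use it, and the stated interpretation depends on doing so. The eligibility difference also means that restricting to self-registrants would not by itself isolate choice.

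**Conclusion.** The concern holds in a limited form. As written, the comparison mixes recruitment channel and eligibility with the choice to join research, and the plan has no means of separating them. The documents support neither the claim that choice plays no part nor the claim that recruitment route can never be recovered.

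The size of the channel part is unknown because the outreach share is not given. Under the assumptions shown (60 versus 120, no true choice effect, non-study registrants all self-registered), it is negligible at a share of about 10%: 5% to 8% false positives for differences of 0.3 to 0.8 SD. At 50% it is material, at 16% to 67%. The eligibility part cannot be sized from the documents.

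This is a secondary descriptive analysis. The pre/post tests of self-efficacy, resourcefulness, financial strain and spending do not depend on it, so the change is worthwhile but not essential.

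**What to change.** 1. Before identifiers are removed, add a recruitment-source variable for every registrant, in and out of the study: self-registered, or registered by or referred from the study team.
2. Make the choice comparison among self-registered caregivers who meet those Section 4.0 criteria that Eventbrite records. State which criteria could not be applied.
3. Describe outreach recruits in a separate column, without reading their difference from the others as an effect of choice.
4. If source cannot be recorded, report the result only as study versus non-study differences.

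The cost is one extra column, filled in while names can still be matched, and a smaller, less precise comparison. At a 50% outreach share the detectable difference rises from about 0.44 to 0.57 SD, before any loss from the eligibility restriction.
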